2.4. Pre- and post-intervention assessments

Once an informed consent is obtained prior to randomisation; participants will be referred to study examiners - a Physical Medicine and Rehabilitation physician, a neurologist, a physical therapist, an occupational therapist and a psychologist, who will not know the treatment group of the patient. They will administer baseline testing during the 2nd and 3rd day after admission to the department (Pre-assessment). The Post-assessment 1 will be done at the end of the three-week inpatient intensive comprehensive rehabilitation (during the last two days of hospitalization). Follow-up assessments will take place 3 and 12 months after the admission, respectively, by a telephone interview and hospital visit for blood draw. The aim is to be assessed only by one examiner, in case of more examiners, inter-rater reliability will be assessed (Table 2).

test	abbreviation	Inclusion and exclusion criteria	Examination No			
			1	2	3	4
			baseli	+3	+3	+ 1
			ne	weeks	month s	year
Neurologist						
Demographic and anamnestic data (age, after first ischemic stroke, days after the stroke) Demographic and anamnestic data (weight and height, cardiovascular risk factors, Bamford classification, medication)			x			
Modified Rankin Scale	mRS	Х		х		
Pre-Stroke Modified Rankin Score	pre-stroke mRS	Х				
Historic Stroke Motor Severity Score	HSSS	Х				
National Institute of Health Stroke Scale	NIHSS	Х				
Psychologist*						
Montreal Cognitive Assessment	MoCA		Х			
Amnesia Light and Brief Assessment	ALBA		х	х		
NEO-Five Factor Inventory	NEO - FFI		х			
Patient-reported Outcomes Measurement Information System Global Health	PROMIS		х	х	х	х
the World Health Organization Disability Assessment Schedule	WHODAS		Х	Х	Х	Х

Table 2: Timing and distribution of examination in the team

the Goal Attainment scale	GAS				
Picture naming and immediate recall	PICNIR	х	х		
Neuro - QOL depression		х	х		
physical therapist					
Hand Dynamometer		Х	Х		
postural tremor		х	х		
Action Research Arm Test*	ARAT	х	х		
Motor Activity Log*	MAL	х	x		
Timed Up and Go*	TUG	х	x		
Berg Balance Scale*	BBS	х	x		
The 10 Metre Walk Test*		x	х		
The 6 Minute Walk Test*		x	х		
Functional Independence Measure*	FIM	х	х		
Laterality index	LI	х			
Nine Hole Peg Test		х	х		
speech therapist*					
The Gugging Swallowing Screen	GSS	Х	х		
The 3F Test – Dysarthric Profile	3F test	х	х	-	
Dysan		х	х		
The Mississippi Aphasia Screening	MAST	х	х		
Test					
Image Naming Test	INT	Х	X		
Blood – Total RNA extraction		х	х	-	
cDNA synthesis					
lncRNA assessment (C2dat1 , GAS5 ,					
MALATI, PARTICLE, H19, MEG3)					

*Tests recommended by General Health Insurance (GHI), Czech Republic.

The qualitative data will be collected in semi-structured interviews with patients as well as clinical specialists with the aim of capturing an extended health evaluation. Specialists will have the possibility to look at the hospital information system, or search in the National Register of Paid Health Services. Data will be captured using an electronic Case Report Form (eCRF) (65).

The following data will be collected:

Demographic and anamnestic data including personal factors (sex, age, education, occupation, social relations, living situation), weight and height, laterality index (66), number of days after the stroke event, personality based on the NEO-Five Factor Inventory (NEO-FFI) (67), pre-stroke functional status based on modified Rankin Scale (68), cardiovascular risk factors (69), the degree of neurological impairment according to the National Institute of Health Stroke Scale (70) and disability with the Modified Rankin Scale (42), Bamford classification of IS based on the initial presenting symptoms and clinical signs (71) as well as pharmacotherapy.

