2.1. Clinical trial design

This will be a Four-Arm Parallel-Group Randomised Double Blinded Controlled Trial with a longitudinal design. Patients who fulfilled inclusion criteria will be randomly assigned to one of the four research groups (Group 1, 2, 3 or 4). Three groups will undergo an inpatient COMIRESTROKE (4 hours/day for 3 weeks). Group 1 (COMIRESTROKE – ICF) will undergo individualised rehabilitation therapy embodying the ICF system as a therapeutic tool, where current needs and wishes of the person after IS are integrated into an interdisciplinary team rehabilitation programme management. Group 2 and 3 will undergo a standard comprehensive intensive rehabilitation program three hours per day (39) plus one hour of specific PT (an individual neuroproprioceptive "facilitation inhibition" for Group 2, a technology-based training for Group 3). Group 4 will undergo standard care and will serve as comparative one to the intensified intervention groups.

Participants will be examined four times (Figure 1). At the beginning and after three weeks of hospitalization (both primary, secondary outcomes and a blood draw will be obtained for total RNA extraction, cDNA synthesis and real-time QPCR assessment of lncRNA candidates previously identified as potential therapeutic influencers in ischemic stroke), and then three months and one year after the end of the program (primary outcomes only).

Figure 1: Design of the study

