2.2. Eligibility criteria and subgroups

Participants will be identified by specialists in neurology and rehabilitation from inpatients at the Department of Acute Care, Department of Neurology, Thomayer University Hospital or University Hospital Kralovske Vinohrady, Prague, Czech Republic.

Inclusion criteria: Adults (18 - 85 years) after the first ischemic stroke in early sub-acute phase (40, 41), with a slight to moderately severe disability [2 - 4 on the Modified Rankin Scale (42)],

with minimal or moderate motor deficit of upper or lower extremities (on NIHSS Item 5 or 6 scores 1–3 points) who were able to perform activities of daily living prior to stroke event [0 – 2 on the Pre-Stroke Modified Rankin Score (43)], with a potential to accept 4 hours of comprehensive rehabilitation per day and to profit from the physiotherapy. Czech is their native language or its knowledge is at the level of the mother tongue.

Exclusion criteria: Low level of consciousness (vegetative state and/or minimally conscious state); severe cognitive decline that would interfere with administration of the tests, premorbid illiteracy, severe visual and/or auditory deficit that would prevent proper completion of the tests; behavioural disorders and/or lack of cooperation with therapist; and severe medical problems with a poor prognosis, (e.g., severe frailty, advanced and incurable cancer, fracture, cardiovascular disorders as chronic heart failure NYHA III, IV, symptomatic coronary artery disease Angina Severity Class III, IV, respiratory insufficiency as chronic obstructive pulmonary disease GOLD IV, and other severe disease) (44).

Randomisation

All patients meeting the above criteria will be invited to participate and asked to provide a written informed consent. They will be randomly assigned (1:1:1:1) as soon as possible, but always within 48 hours of admission, into one of the four interventions (represented by Group 1, 2, 3 or 4) using offsite-independent randomization protocols (www.randomization.com). Concealed allocation will be performed using sequentially numbered opaque sealed envelopes only accessible by research personnel with no involvement in the trial.

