2.5. Outcomes and measures

2.5.1. Primary Outcomes

- PROMIS Global Health is a 10-item scale which asks the patient to assess (self-report) their physical, mental and social health in the past 7 days (72, 73).
- WHODAS 2.0 is a generic assessment instrument developed by WHO to provide a standardized method for measuring health and disability. It is grounded in the conceptual framework of the ICF and integrates an individual's level of functioning in major life domains and directly corresponds with ICF's "activity and participation" dimensions. The 36-item version will be used. Higher score means higher disability (74).
- GAS is an individualized outcome measure involving goal selection and goal scaling that is standardized in order to calculate the extent to which patient's goals are met. Each goal is rated on 5-point scale (-2 much less than expected, 0 achieved the expected level, 2 much more than expected (75, 76).

Three types goals will be established:

A. Overarching long-term goal (Global Goal, G) that reflects a desired improvement on the level of participation: usually restoration of previous life including remunerative employment, sport and leisure activities (interview by call at 3 and 12 months follow up).

B. Mid-term goal (Program Goal, P) that reflects improvement mainly in the domain of activities and participations achievable by the rehabilitation program: restoration of self-care, (almost) independence in daily living etc. (interview by call at 3 months follow up)

C. Three Short-term goals (Cycle Goals C1, C2, C3) mainly in the domain of functioning and activities. Usually specific, most problematic components of the Program Goal (evaluated by the rehabilitation team together with the rehabilitant).

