2.9. Measuring the effectiveness of rehabilitation

To test hypothesis I., i.e., a positive influence on all outcomes, the effect of therapy for each therapeutic group will be assessed separately by paired t-tests performed on pre-test and post-test scores. The Wilcoxon rank test will be used on data where normal distribution cannot be expected.

To test hypotheses II. and III, a comparison between therapeutic groups will be performed using two sample Student t-tests on differences between measurement time points (or Wilcoxon tests respectively for data, where normal distribution of the differences cannot be expected). For hypothesis II, the COMIRESTROKE - ICF group will be compared against the rest of the participants. For hypothesis III, the COMIRESTROKE - NEFI group will be compared against the rest of the participants. A one-sided alternative will be tested according to our hypotheses. We will also implement the one-way ANOVA test to jointly compare all three groups for prepost differences. In addition, a Tukey post-hoc comparison will be made to detect any further group differences beyond our hypotheses.

To assess the overall impact of rehabilitation and to compare effectiveness of different therapeutic approaches for Hypotheses I – III in more complex way, and to test for effect of other covariates in Hypothesis IV, a linear mixed effect model will be used with random patient effect fitted to longitudinal patient data. Measurement effect, group effect and their interaction, as well as effects of other covariates such as the level of disability in admission time will be tested by F test.

To address Goal I, correlations between changes in different examination scores will be evaluated using Pearson correlation coefficient and its nonparametric analogies. A cluster analysis will be performed to identify different phenotypes. This will allow the identification of different groups of patients in relation to the efficacy of the neuro-rehabilitation programs.

To address Goal II, for selected multi-item instruments, item-response theory (IRT) and generalized linear regression models will be used to study differential item functioning with respect to rehabilitation groups. Account will be taken for other respondent characteristics. Use will be made of differential item functioning in change (DIF-C) analysis (7) in order to detect between-group differences.

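### The timing rules for randomisation and baseline testing allow the PROMIS and WHODAS baselines to be taken after allocation

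*Combined protocol and SAP*

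**What the plan says.** All references are to the combined protocol and SAP.

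- **Randomisation (section 2.2).** "They will be randomly assigned (1:1:1:1) as soon as possible, but always within 48 hours of admission". Sealed opaque envelopes conceal the sequence.
- **Baseline (section 2.4).** "Once an informed consent is obtained prior to randomisation; participants will be referred to study examiners". The examiners are people "who will not know the treatment group of the patient". On timing: "They will administer baseline testing during the 2nd and 3rd day after admission to the department (Pre-assessment".
- **Instruments (section 2.5.1 and Table 2).** PROMIS and WHODAS are primary outcomes and are marked at baseline. PROMIS is a scale that "asks the patient to assess (self-report) their physical, mental and social health in the past 7 days". How WHODAS is administered is not stated.
- **Masking (section 2.1).** "This will be a Four-Arm Parallel-Group Randomised Double Blinded Controlled Trial with a longitudinal design". The text describes blinding of the examiners (2.4) and of the laboratory samples (2.5.3). It does not say that patients are masked, or how.
- **Analysis (sections 2.7 and 2.9).** Hypotheses II and III use "two sample Student t-tests on differences between measurement time points", one-sided, comparing the ICF or the NEFI group with everyone else. Baseline differences, if seen, are to be handled in the longitudinal models.

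**The concern.** Consent is the only step that the plan places before randomisation. Nothing requires the baseline to be finished before the envelope is opened or before the patient learns the result. Blinding the examiner does not protect an answer that the patient gives about himself or herself. The four programmes are also easy to tell apart: joint goal setting, robotic or virtual-environment training, Vojta or Bobath therapy, and standard care on the neurology ward (section 2.3).

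If knowledge of the arm, or early treatment, shifts the baseline in one arm, a change score carries that shift in full. The group-by-measurement interaction in the mixed model has the same weakness, because the baseline is its first measurement. Adjusting for the baseline does not repair this. If allocation caused the difference, the covariate is a post-randomisation variable, and the adjustment suggested in section 2.7 may remove or add effect.

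**Working it through.** **1. Timing.** The two day windows are converted to hours since admission, for any time of admission, and set against the 48-hour limit.

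| Counting rule | 2nd day | 3rd day |
|---|---|---|
| Admission day is day 0 | about 24 to 72 h | about 48 to 96 h |
| Admission day is day 1 | about 0 to 48 h | about 24 to 72 h |

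Under day-0 counting, all 3rd-day testing falls after the latest permitted randomisation. Under day-1 counting with tests between 08:00 and 16:00, the 3rd day covers 32 to 64 h, so testing may fall on either side of the limit. Because allocation is to be as early as possible, it may also precede 2nd-day testing. Under both rules a post-allocation baseline is possible. Under neither is it forced for PROMIS and WHODAS, which could be given early on the 2nd day. Section 2.4 also counts from admission to the department. If that is a later transfer, the baseline moves later still.

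**2. The plan's own figure.** Section 2.6 gives 70 per group for d = 0.5, α = 0.05 and power 0.80. The two-sided normal formula gives 2 × (1.960 + 0.842)² / 0.5² = 62.8, so 63. A value of 70 would follow from an unstated 10% allowance for loss (63 / 0.9 = 70). The present point does not depend on this figure. It is noted only because arm sizes are needed below, and section 2.6 gives 210 in total for what are four groups.

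**3. Effect on the planned test.** Inputs:
- 210 patients split 1:1:1:1, so 210 / 4 = 52.5, or about 53 against 157 (reading the comparison as one arm against the other three);
- one-sided 5% level, taken as the conventional 0.05 for the tests in 2.9, critical value 1.645;
- an assumed shift b of 0.1 to 0.2 SD of the change score, in the tested arm only. The documents give no figure for b.

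Scale factor: k = √(53 × 157 / 210) = 6.29. With no true effect, the rejection rate is P(Z > 1.645 − bk) if the shift favours the tested arm, and P(Z > 1.645 + bk) if it goes against it.

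| b | bk | Favours tested arm | Against tested arm |
|---|---|---|---|
| 0.1 | 0.63 | P(Z > 1.016) = 15.5% | P(Z > 2.274) = 1.1% |
| 0.2 | 1.26 | P(Z > 0.386) = 35.0% | P(Z > 2.904) = 0.2% |

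With 70 per group in four groups (70 vs 210, k = √(70 × 210 / 280) = 7.25) the ranges are 18% to 42% and 0.9% to 0.1%.

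**4. Cost in power when the shift goes against the tested arm.** If the true effect is 0.5 SD, power is P(Z > 1.645 − (0.5 − b) × 6.29): 93% at b = 0, 81% at b = 0.1 and 60% at b = 0.2. Section 2.6 ties its 0.5 to the Berg Balance Scale, so its use for PROMIS or WHODAS is an assumption.

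**5. Units.** The SD of a change is the baseline SD times √(2(1 − ρ)). A shift in baseline SD equals the same shift in change-score SD only when the pre-post correlation ρ is 0.5.

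**The case against.** The strongest reply has four parts.

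- **The order is unclear, not wrong.** Section 2.4 can be read as referral to the examiners before randomisation, and it calls the baseline a pre-assessment. This stands in part. A reader might infer that some of the PROMIS or WHODAS baseline must follow allocation, and the day counts do not support that. They do allow it, and nothing in the text prevents it.
- **Patients' knowledge is inferred.** The trial is labelled double-blinded, and no section says when patients are told or when therapy starts. This stands as a limit. It would go beyond the documents to say that patients know their arm, or have begun treatment, at baseline. It remains a fair risk because no masking of patients is described.
- **The direction may be the reverse of the feared one.** Hope or early treatment in a favoured arm would improve its baseline and shrink its change. Disappointment in standard care would worsen that group's baseline and enlarge its change. Both work against the tested arm. If only Group 4 shifts, it is one of three pooled comparators and the contrast moves by b/3: P(Z > 1.645 + 0.21) = 3.2% and P(Z > 1.645 + 0.42) = 1.9%. This stands, so a reader should not infer that false positives are necessarily inflated. Nor is there a planned one-sided test of one arm against another: pairs of groups are compared by Tukey's method.
- **The seven-day recall of PROMIS dampens any shift.** It may, but it does not remove the effect of expectation on the answers.

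**Conclusion.** The point holds as a possibility that the plan's own timing rules create. PROMIS and WHODAS baselines can be taken after allocation, in patients for whom no masking is described, and any resulting difference enters the change-score contrasts for hypotheses II and III in full.

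Neither the direction nor the size is known. For an assumed 0.1 to 0.2 change-score SD confined to the tested arm, at 53 vs 157, the one-sided error rate moves from 5% to about 15% to 35%, or down to about 1.1% to 0.2% with a matching loss of power. These figures show sensitivity and do not predict a bias. The amendment should be made because it is cheap and the affected outcomes are primary.

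The point does not extend to GAS goal setting. Section 2.3 describes Group 1's goals as built on a functional profile after randomisation, as part of that arm's programme, and Table 2 as it reads here shows no baseline mark for GAS.

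**What to change.** Reconcile sections 2.2 and 2.4. State in both that the PROMIS and WHODAS baselines are completed before the envelope is opened, within the existing 48 hours. State also when patients are told their allocation, and whether the two uses of admission mean the same event.

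The performance, speech and cognitive tests by blinded examiners can stay on the 2nd and 3rd day, and Group 1's ICF goal setting can stay after allocation.

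The cost is one questionnaire sitting moved earlier, with the same instruments and staff. For some patients the envelope is opened a few hours later, still inside the permitted window. The sample size does not change. If the sites already work in this order, a sentence in each section is enough.

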2.5. Outcomes and measures

2.5.1. Primary Outcomes

- PROMIS Global Health is a 10-item scale which asks the patient to assess (self-report) their physical, mental and social health in the past 7 days (72, 73).
- WHODAS 2.0 is a generic assessment instrument developed by WHO to provide a standardized method for measuring health and disability. It is grounded in the conceptual framework of the ICF and integrates an individual's level of functioning in major life domains and directly corresponds with ICF's "activity and participation" dimensions. The 36-item version will be used. Higher score means higher disability (74).
- GAS is an individualized outcome measure involving goal selection and goal scaling that is standardized in order to calculate the extent to which patient's goals are met. Each goal is rated on 5-point scale (-2 much less than expected, 0 achieved the expected level, 2 much more than expected (75, 76).

Three types goals will be established:

A. Overarching long-term goal (Global Goal, G) that reflects a desired improvement on the level of participation: usually restoration of previous life including remunerative employment, sport and leisure activities (interview by call at 3 and 12 months follow up).

B. Mid-term goal (Program Goal, P) that reflects improvement mainly in the domain of activities and participations achievable by the rehabilitation program: restoration of self-care, (almost) independence in daily living etc. (interview by call at 3 months follow up)

C. Three Short-term goals (Cycle Goals C1, C2, C3) mainly in the domain of functioning and activities. Usually specific, most problematic components of the Program Goal (evaluated by the rehabilitation team together with the rehabilitant).

2.5.2. The secondary outcomes

The secondary outcomes include clinical tests and questionnaires of physical functions and functional independence (examined by an independent physical therapist), speech and swallowing (examined by an independent speech therapist), cognitive and psychological functions (examined by an independent clinical psychologist).

2.5.2.1. Physical functions and functional independence

Upper extremity functions

• Jamar Hydraulic Hand Dynamometer will be used to measure isometric grip force from 0-90 kg. Five handle positions from 35-87 mm will be tested. The measurement is in kg (the higher the value, the better the function) (77).

• A postural tremor will be measured by the 3-axis accelerometer and 3-axis gyroscope chip (Motion Tracking sensor MPU-6050) which can measure acceleration up to 16 g and rotation up to 2000 degrees per second. The sensor will be fixed to the patient using a ring on a finger during stretching the whole arm forward, separately passed for the left and right hand and with opened and closed eyes (one-minute measurement for each position). Data from the chip will be acquired by an own measuring device with microcontroller Atmel Mega 328 and stored on an SD card.

For the signal analysis, the magnitude of acceleration – the root of sum of each component squares – will be computed from separate axes. The sampling frequency will be 100 Hz. Thus, four signals with 6000 samples will be recorded for each patient – records of postural tremor for right/left hand with opened/closed eyes.

For each record, the signal of acceleration will be filtered by a filter of isoline (typically by high-pass 2^{nd} order Butterworth filter with cut-off frequency of 0.5 Hz). Consequently, the power spectral density (PSD) will be estimated.

The spectral characteristic will be parameterized by selected parameters, for example f_{MAX} (a frequency for which the smoothed PSD is maximal - lower value, lower tremor) or $P_{\text{fl-f2}}$ (a power of the signal in band from f_1 to f_2 - lower value, lower tremor) (78).

- Nine Hole Peg Test is used to measure finger dexterity. A client takes the pegs from a container, one by one, and places them into the holes on the board, as quickly as possible. Shorter times reflect better function (79).
- Action Research Arm Test (ARAT) is a 19 item observational measure to assess upper extremity performance (coordination, dexterity and functioning). Items are categorized into four subscales (grasp, grip, pinch and gross movement). A higher score means better function (80).
- Motor Activity Log is a scripted, structured interview to measure real-world upper extremity function consisted of 14 activities of daily living such as using a towel, brushing teeth, and picking up a glass. A higher score means better function (81).

Mobility and walking

- Timed Up and Go is a simple performance-based measure of dynamic balance. The subject stands up from a chair, walks 3m, turns back, and sits down again as quickly and safely as possible while being timed. Shorter times reflect better mobility (82).
- Berg Balance Scale is a 14-task scale that requires subjects to maintain their balance in positions and tasks of increasing difficulty. A lower score means worse balance (83).
- The 10 Metre Walk Test is a performance measure used to assess walking speed in meters per second over 10 meters. Shorter time reflects better mobility (84).
- The 6 Minute Walk Test is a long walking capacity test recording the maximal distance a subject can walk at the fastest speed possible in 6 minutes. The more distance covered, the better the walking performance is (84).

Functional Independence

Functional Independence Measure is an 18-item measurement tool which explores an individual's physical, psychological and social function. It uses the level of assistance an

individual needs to grade functional status from total independence to total assistance. The higher the score, the better (higher independence) (85).

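### Taking the three-axis magnitude with gravity still in the signal records mainly the tremor component along gravity, and peak frequency is labelled as a measure of tremor amount, which it is not

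*Combined protocol and SAP*

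**What the plan says.** Section 2.5.2.1 records postural tremor with a finger-worn chip that holds a 3-axis accelerometer and a 3-axis gyroscope. The arm is held forward, each hand is tested separately, and eyes are open or closed, with a "one-minute measurement for each position". The processing is described in this order:

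1. "the magnitude of acceleration – the root of sum of each component squares – will be computed from separate axes".
2. "The sampling frequency will be 100 Hz", and hence "four signals with 6000 samples will be recorded for each patient".
3. In a new paragraph, "the signal of acceleration will be filtered by a filter of isoline", typically a 2nd-order Butterworth high-pass at 0.5 Hz. The power spectral density (PSD) is then estimated.
4. Two example parameters are given. The first is f_MAX, described as "a frequency for which the smoothed PSD is maximal - lower value, lower tremor". The second is power in a band from f1 to f2, with the same direction label and no values for the band limits.

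The section does not mention gravity, tilt, or any use of the gyroscope in the analysis. Table 2 (section 2.4) places the test at baseline and three weeks.

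**The concern.** There are two separate problems.

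First, the magnitude is a non-linear step. With the constant 1 g still in the signal, acceleration perpendicular to gravity changes the length of the vector only to second order. A high-pass filter applied afterwards cannot restore what the magnitude has removed. Tremor power then depends on the direction of the tremor as well as its size. The plan fixes the arm position but not forearm rotation, so the same wrist movement could be mainly vertical at one visit and mainly horizontal at the next.

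Second, f_MAX says how fast the dominant oscillation is, not how large. Calling a lower value less tremor gives it a clinical direction that its definition does not support. Section 2.9 plans one-sided tests for hypothesis III, which covers secondary outcomes. If f_MAX is tested there, the label would set the tail.

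**Working it through.** **The plan's own figures.** 100 Hz × 60 s = 6000 samples, and 2 hands × 2 eye conditions = 4 signals. Both reproduce. Four signals means one scalar per record; keeping three axes would give 12. This supports reading the magnitude as taken before the filter.

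**Assumptions not in the documents.** The sensor reads 1 g at rest (9.81 m/s²). Tremor is a single sinusoid of 4 to 8 Hz along a fixed line, with amplitude 0.02 to 0.2 g (0.1 to 5 m/s² in a second set of runs). Power is summed over 1–20 Hz.

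**Algebra.** Let v be acceleration along gravity and h perpendicular to it. Then

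√((g+v)² + h²) ≈ g + v + h²/(2g).

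The v term passes unchanged. If h is a sinusoid of amplitude a, h²/(2g) is a constant plus an oscillation of amplitude a²/(4g) at twice the frequency.

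**Power retained.** For a tremor of amplitude A at angle θ from vertical, the first-order term is A·cos θ, so the share of power kept is about cos²θ. The written steps were simulated at 6 Hz and 0.1 g (100 Hz, 60 s, magnitude, 0.5 Hz high-pass, Welch PSD) and compared with the sum of the three per-axis PSDs:

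| Angle from vertical | cos²θ | Simulated share kept | Peak |
|---|---|---|---|
| 0° | 100% | 100% | 6 Hz |
| 30° | 75% | 75% | 6 Hz |
| 45° | 50% | 50% | 6 Hz |
| 60° | 25% | 25% | 6 Hz |
| 75° | 6.7% | 6.7% | 6 Hz |
| 88° | 0.12% | 0.18% | 6 Hz |
| 89° | 0.03% | 0.09% | 12 Hz |
| 90° | 0% | 0.06% | 12 Hz |

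At exactly 90° the share kept is (A/4g)². At 0.2 g this is 0.05² = 0.25% (1/400); at 0.02 g it is 0.005² = 0.0025% (1/40,000).

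**When the peak doubles.** The second-order term must exceed the first-order one: A·cos θ < A²·sin²θ/(4g). With A in units of g, this is cos θ < (A/4)·sin²θ. The threshold is 87.1° at 0.2 g, 88.6° at 0.1 g and 89.7° at 0.02 g. The simulation agrees.

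**The other order.** Filtering each axis and then taking the magnitude rectifies the signal. In the noise-free runs at 5 Hz the peak came out at 10 Hz in every case, including purely vertical tremor.

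**f_MAX and amount.** For vertical tremor, where the written pipeline works, power is A²/2:

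- 4 Hz at 2 m/s²: f_MAX 4 Hz, power 2.
- 4 Hz at 0.2 m/s²: f_MAX 4 Hz, power 0.02.
- 8 Hz at 0.2 m/s²: f_MAX 8 Hz, power 0.02.

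The first two differ 100-fold in power and score the same on f_MAX. The third has one hundredth of the power of the first and scores as more tremor.

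**Cost of the per-axis alternative.** A pure rotation of ±δ leaves the magnitude at 1 g, so its oscillating power is zero. It moves gravity between axes, however, with amplitude of about g·sin δ. At ±2° that is 0.035 g and at ±5° it is 0.087 g, both within the assumed tremor range. Simulation at 6 Hz gives the same values.

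**The case against.** The plan is not rigid. The filter is only typical, the parameters are examples, band power is already listed, and the tremor method rests on a cited source that was not available for this review. That leaves room to correct the method, but it does not make the written order or the f_MAX label right.

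The magnitude also has a real merit: it ignores tilt and does not depend on how the ring sits on the finger. This stands, and it limits the remedy.

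Several stronger readings are tempting but are not supported:

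- A reader might infer that reported frequencies are generally doubled. That happens only for almost wholly horizontal tremor; otherwise the error is lost power.
- A reader might take the 400- to 40,000-fold loss as the expected error. It is the limiting case at 90°, and the documents give no horizontal share of tremor.
- A reader might conclude that sensor orientation biases the result. Only the direction of tremor relative to gravity matters. Nothing in the documents shows that this changes between visits. If it changed similarly in all arms, between-arm comparisons would mainly lose sensitivity; within-group paired tests are more exposed.
- A reader might say that f_MAX never responds to amount. With an assumed low-frequency background of 0.02 g SD, halving a 6 Hz tremor from 0.01 to 0.005 g moved f_MAX from 6.0 to 1.3 Hz. It can drop when tremor sinks below background, but this is a threshold effect, not a graded one.

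**Conclusion.** The point holds on both counts, with limited reach.

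As written, the pipeline measures tremor along gravity correctly and loses the rest: about half the power at 45°, three quarters at 60°, and more than 99.7% when tremor is purely horizontal at 0.02 to 0.2 g. This rests on the order of steps in section 2.5.2.1, on the count of four scalar signals, and on the fact that an accelerometer senses gravity. The cos² rule does not depend on the assumed frequency and depends only weakly on amplitude; the doubling threshold does depend on amplitude.

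The f_MAX criticism needs none of these assumptions. Multiplying a signal by a constant leaves the frequency of its spectral peak unchanged, so the direction label is unsupported as written.

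Tremor is one of many secondary measures, and no hypothesis in section 2.8 names it. The primary outcomes and the sample size are unaffected.

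**What to change.** 1. Remove the better/worse direction from f_MAX and report it descriptively. Name band power as the measure of tremor amount and state f1 and f2 before analysis. This costs only a change of text.
2. Confirm whether the SD card keeps the three raw axes and the gyroscope channels. The section says that chip data are stored, but the only record it counts is four signals per patient, so retention of the axes should not be assumed. Axes that were not saved cannot be recovered.
3. If they are kept, remove gravity before combining axes, for example by using the gyroscope to correct for tilt. Then high-pass each axis, estimate its PSD and sum the three. The filtering and summing are a few lines of code; the tilt correction is more work and needs its own specification. No patient contact changes.
4. Do not filter each axis and then take the magnitude, because that doubles the frequency.
5. If tilt cannot be corrected, keep the magnitude and state that it captures mainly tremor along gravity. An uncorrected per-axis sum would read a ±2° rotation at 6 Hz as about 0.035 g of tremor.
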